6.2. Patient Population

6.2.1. Sample Size

Up to 60 patients with resectable or borderline-resectable pancreatic ductal adenocarcinoma (PDAC) cancer who may be considered candidates for surgical resection without or with neoadjuvant treatment will be enrolled in the study.

6.2.2. Inclusion Criteria

Patients must meet **ALL** criteria listed below for entry:

1. Patients with pathologically confirmed pancreatic ductal adenocarcinoma.
2. Treatment-naïve
3. Staged as resectable or borderline-resectable
4. Planned to undergo surgical resection or to receive neoadjuvant therapy (i.e., chemotherapy, radiation therapy, or combination) and subsequent planned surgical resection
5. Anatomic imaging (e.g., CT, MRI) obtained within ≤ 28 days of consent
6. Age ≥ 18 years
7. Completed informed consent as determined per the IRB of record

6.2.3. Exclusion Criteria

Patients will be excluded from entry if **ANY** of the criteria listed below are met:

1. Pregnant as determined by a pregnancy test as per institutional guidelines for individuals of child-bearing potential
2. Declining to use effective contraceptive methods during the study (for individuals of child-producing potential)
3. Need for emergent surgery that would be delayed by participation
4. Bacterial, viral, or fungal infections requiring systemic therapy, that are expected to impact FAP expression in the opinion of the sponsor or their designee
5. Serious co-morbidities and serious nonmalignant disease (e.g., hydronephrosis, kidney failure, liver failure, systemic or local inflammatory or autoimmune diseases or other conditions) that in the opinion of the investigator, physician of record and/or Sofie could compromise patient safety and/or protocol objectives
6. Known diagnosis of an autoimmune disorder, that is expected to impact FAP expression in the opinion of the sponsor or their designee
7. Patients receiving any other investigational agent within the past 28 days
8. Breastfeeding. Note: nursing parents are allowed if the potential participant commits to pumping breast milk and discarding it from injection to ≥ 24 hours from the time of the [^{68}Ga]FAPI-46 injection.
9. Known hypersensitivity to any excipients used in [^{68}Ga]FAPI-46: trace amounts of sodium acetate sodium ascorbate and/or hydrochloric acid

6.2.4. Concomitant Medication

No other investigational medical products are allowed during this study, from eligibility determination to surgery. Participant may receive investigational medical products post-surgery for the purposes of another clinical trial.

Drugs used off-label consistent with institutional practice, standard of care, or practice of medicine do not meet the definition of investigational medical product.

Participants should receive full concomitant care during this clinical trial consistent with institutional practices and standard of care.

6.3. Study Intervention

6.3.1. [⁶⁸Ga]FAPI-46

FAPI-46 precursor is reacted with gallium-68 to produce the final drug product [⁶⁸Ga]FAPI-46. The resulting material contains buffering excipients that maintain the stability to produce the [⁶⁸Ga]FAPI-46 final drug product.

6.3.2. Dosing and Administration

Intravenous administration of radiolabeled [⁶⁸Ga]FAPI-46 (5 mCi \pm 2 mCi) as per institutional policies, administered 15 minutes (\pm 10 minutes) prior to the initiation of the attenuation correction CT.

6.3.3. Preparation, Handling, Storage, and Accountability

- **Acquisition and accountability**

An accurate and current accounting of the precursor and/or study drugs will be maintained utilizing an ALCOA compliance drug accountability record (DAR) that will be verified by the Sponsor's study monitor.

Drug accountability will be documented using the study's drug accountability and receipt form (DARF) or the investigational site's template *if* deemed acceptable by the sponsor and/or designee. Documentation confirming review and approval of the Site's template must be provided by Sponsor or designee and filed within the ISF.

At minimum:

- Receipt: date received and signature/mark individual confirming receipt
- Dispensing: date, quantity of IMP (both in ml and mCi), study identification number and initials of participant, and signature/mark of individual confirming these dispensing details.
- Investigational medical product destroyed, where 'destroyed,' is equivalent to allowing decay for 10 half-lives and then destroying the physical component consistent with institutional policy & procedure.

The DAR will be monitored against study drug and supply shipments and ALCOA.

Drug components provided by the Sponsor or designee must be used only for this study. Accountability logs must be utilized to track drug components.

Only authorized prescribers may prescribe the investigational medical product ⁶⁸Ga-FAPI-46.

- **Authorized prescribers must be authorized users as per NRC.**

A copy of the prescription must be kept on file in the participant's medical record or, if precluded by institutional policy, within the study binder.

- **Formulation, appearance, packaging and labeling**

The final [^{68}Ga]FAPI-46 drug product (DP) is a clear, colorless, and particulate free, sterile solution supplied in 10 mL Type 1 glass vial. The DP contains 0.1 mCi/ml to 5.0 mCi/ml [^{68}Ga]FAPI-46 at the end of synthesis (EOS) and 11.81 mg/mL Sodium Acetate and 0.49 mg/mL Sodium Ascorbate in sterile water for injection in approximately 9.9 mL.

- **Storage and stability**

Stored upright in lead-shielded container at 15 – 25 °C with use before expiration of 4 hours post end of synthesis (EOS). Handling of the investigational medical product is subject to radioactive material regulations and licensing requirements.

- **Preparation**

[^{68}Ga]FAPI-46 is provided as ready to use vial or syringe. No further preparation or manipulation is required. The dose will be administered to the patient according to the site's standard operating practices.

6.3.4. Intervention Compliance

All interventions in this protocol are administered by licensed medical staff under the supervision of the study investigator. For this reason, adherence to protocol will be assessed through source document verification in the electronic health records for:

- Prescription, dispense, and administration of [^{68}Ga]FAPI-46
- Scan settings (e.g. bed positions, field of view settings)

6.4. Study Intervention Discontinuation and Participant Discontinuation/withdrawal

6.4.1. Discontinuation of Study Interventions

Participants who withdraw after consenting to the clinical trial, but do not receive an injection of [^{68}Ga]FAPI-46, will not be followed for this clinical trial.

Participants who withdraw after receiving at least 1 injection of [^{68}Ga]FAPI-46 but who are not scanned will be followed as an intent-to-treat population for the purposes of safety assessments. If the participant withdraws full permission (i.e., revokes HIPAA authorization), the participant will not be followed further, but all data obtained until the date of HIPAA revocation will be used for the purposes of this study. Participant's intent must be well documented in the case book.

A participant's discontinuation of the study intervention (i.e., declining the second [^{68}Ga]FAPI-46 scan for Cohort 2) does not immediately define the subject as being off-study. **The Sponsor should be contacted to determine if study procedures should continue should the participant consent to it.** Participants who decline further intervention (i.e. scans) should be evaluated by the Sponsor as an unanticipated problem and/or serious adverse event.

Scenarios for study intervention discontinuation:

- **Participant declines further study intervention.** If a participant who has received at least one injection of [^{68}Ga]FAPI-46 declines further study intervention, the reason for declining further participation should be documented – specifically, if it is due to an adverse event.
- **Unforeseen medical event.** If a participant undergoes a medical event that compromises the subject's safety or study's endpoints, the participant may be withdrawn from treatment. The sponsor or investigator may make this determination. If a participant is withdrawn for this reason, the

subject must be followed for a minimum of 24 hours from the last injection with investigational product.

- **Pregnancy.** If a participant declares pregnancy, the participant will be withdrawn from study procedures. The Sponsor will be notified within 1 business day of the event. The participant should be asked to consent to have the pregnancy followed (as appropriate).
- **Participant non-compliance.** If a participant does not comply with the required adverse event assessment (i.e., hematologic and serum chemistry assessments, follow-up assessments), study treatment may be discontinued to reduce risk to the participant.

6.4.2. Participant Discontinuation / Withdrawal from the Study

Subject participation in the study may be discontinued entirely (i.e. withdrawn from study without further follow-up or interaction) in the following circumstances:

- **Participants who decline to receive any study intervention after consenting** to the clinical trial are withdrawn from study and are not followed for this clinical trial.
- **Investigator non-compliance.** If an investigator is considered to be non-compliant with the study protocol or federal, state, local, or institutional requirements, the sponsor may end the study and withdraw subjects from trial.
- **Participant's refusal to continue.** Participants who decline further study follow-up (i.e. no longer wish to undergo study assessments) are withdrawn from the study. If the participant withdraws full permission (i.e., revokes HIPAA authorization), the participant will not be followed further, but all data obtained until the date of HIPAA revocation will be used for the purposes of this study. Subject's intent must be well documented in the case book.
- **Termination of study.** If the study is terminated for any reason, the participant will be followed for a minimum of 24 hours from the last injection of [⁶⁸Ga]FAPI-46 for safety assessment, including hematologic and serum chemistries as prescribed per protocol.

The reason for participant discontinuation or withdrawal from the study will be recorded in the subject's casebook and entered into the electronic data capture system (EDC).

6.4.3. Lost to Follow-Up

The following actions must be taken if a participant fails to return to the clinic for a required study visit:

- **Imaging Visit.** If the participant fails to maintain the scheduled appointment for the ⁶⁸Ga-FAPI-46, and the investigational medical product is wasted, the site will contact the Sponsor or designee. The Sponsor or designee will determine if the participant should be removed from study or be allowed the opportunity to be rescheduled.
- **Safety follow-up.** The investigator or designee will make every effort to regain contact with the participant (where possible, 3 telephone calls and, if necessary, a certified letter to the participant's last known mailing address or local equivalent methods). These contact attempts should be documented in the participant's medical record or study file.

Should the participant continue to be unreachable, he or she will be considered to have withdrawn from the study with a primary reason of lost to follow-up.

6.4.4. Replacement Criteria

Participants who have withdrawn or are withdrawn from study may be replaced at Sponsor's discretion.

7. STUDY ASSESSMENTS AND PROCEDURES

An overview of the study schedule is provided in tabular form under "SCHEDULE OF EVENTS." The timing of each visit will be relative to prior visit. Individual study procedures are described below in Section 7.1.

7.1. Study Procedures

7.1.1. Informed Consent

Informed consent will be obtained prior to undertaking any protocol-specific research-only procedures. All participants must provide informed consent as outlined by the IRB of record. No elements of consent will be waived and will be compliant with U.S. FDA federal code.

If written consent is used, the participant must receive a copy of the signed informed consent form. If oral consent is used, the participant must be provided documentation as outlined by the IRB of record. Documentation of the consent process must be maintained in the participant's medical record or the participant's case history, dependent upon institutional policies.

7.1.2. Contraception

For individuals of child-bearing potential, effective contraception must be utilized during the study. Effective contraceptives include abstinence as well as barrier and oral contraceptives.

If participants are engaging in fertility sparing strategies (i.e. ova collection and banking, sperm collection and banking), this should be done prior to injection of study agent.

Participants should not discontinue contraceptive strategies without speaking with their treating oncologists.

7.1.3. Medical and Surgical History

The following should be documented in the participant's case history and reported through the EDC:

- Medical history related to fibroinflammatory diseases, cancers, or any conditions which may impact uptake of the study drug, as documented in the medical record for the 5 years (e.g. such as non- rheumatoid arthritis, gout, edema). Medical history should provide explanation / justification for any active treatments and concomitant therapies taken at study entry.
- Known allergies
- History of myocardial infarction or other life-threatening event, regardless of time-frame.
- Race and ethnicity; if participant declines, this should be clearly noted in the case history.
- Any prior radiation and its indication.

7.1.4. Concomitant Medications

For the purposes of this protocol, a concomitant therapy is considered to be any of the following:

- Prescription medication from an authorized prescriber
- Over the counter medications
- Complementary or alternative medications, including herbal remedies or supplements

A concomitant medication log, separate from the participant's medical chart, will be maintained for the purposes of this trial. This log will be a source document and must meet ALCOA standards. Appropriate medical staff will review concomitant medications at each study visit with the subject so the medications can be reviewed if an untoward event occurs during the study.

All concomitant medications and supportive therapy administered from consent (i.e. routine medications) through end of must be reported using on the appropriate case report form (eCRF).

7.1.5. Routine and Symptom Directed Physical Examination

A physical examination is required per protocol for study eligibility during the screening window. At minimum, the physical examination includes examination of major body systems, including general appearance, skin, neck, head, eyes, ears, nose, throat, heart, lungs, abdomen, lymph nodes, extremities and nervous system.

A symptom focused physical exam is performed as needed during the adverse event window 24 to 72 hours post-injection of [⁶⁸Ga]FAPI-46. This physical exam would be performed to further characterize an observed adverse event for study documentation. The adverse event or concern triggering symptom-focused physical exam should be clearly documented.

7.1.6. Vital Signs

For protocol, collected vital signs are blood pressure, heart rate, respiratory rate, temperature, and weight. Vital signs must be obtained after sitting at least two minutes; time seated and time obtained must be documented. Height is collected at screening only.

On day of [⁶⁸Ga]FAPI-46, a set of VS must be obtained prior to injection and post-injection prior to discharge.

7.1.7. Performance Status

Performance status will be assessed using ECOG performance status criteria as outlined in Appendix 2.

7.1.8. Clinical Laboratory Tests

Local laboratories will analyze all hematology, blood chemistry collected for the study. Samples will be analyzed at a facility meeting Clinical Laboratory Improvement Amendments (CLIA) requirements and/or using methods documented in a methods validation report.

7.1.9. CBC with differential

White blood cell count, red blood cell count, hematocrit, hemoglobin, platelets, absolute neutrophil count, lymphocytes, basophils, eosinophils, and monocytes will be collected at screening and per the schedule of events.

CBC w/diff must be resulted prior to injection with [⁶⁸Ga]FAPI-46.

7.1.10. Serum Chemistry

Glucose (non-fasting), sodium, potassium, chloride, carbon dioxide, magnesium, calcium, blood-

urea-nitrogen (BUN), creatinine, aspartate aminotransferase, alanine aminotransferase, alkaline phosphatase, total protein, albumin, and total bilirubin.

7.1.11. Pregnancy Test(s)

A urine pregnancy test will be performed for individuals of child-bearing potential at screening and prior to injection of [^{68}Ga]FAPI-46 as per institutional policies, but no more than 72 hours of dosing study drug.

If the urine pregnancy test is inconclusive, a blood test must be ordered and resulted as negative prior to injection of [^{68}Ga]FAPI-46.

An individual who has recently undergone an abortive procedure may still have elevated hCG levels. In this situation, documentation from a treating physicians that the patient is not pregnant will suffice *in lieu* of a pregnancy test.

7.1.12. [^{68}Ga]FAPI-46 PET Scan

The imaging manual contains detailed technical information for the [^{68}Ga]FAPI-46 PET/CT Scan.

7.1.13. Prior Preparation

Participants should be directed to hydrate well the day prior to scan. The scan does not require fasting but participants are asked to abstain from alcohol and supplements ~ 1 day prior to scan. Participants should rest well the night before the scan.

7.1.14. Day of Scan

Obtain vitals (section 7.1.5) prior to initiating procedures to reduce stress-associated elevations.

[^{68}Ga]FAPI-46 is administered intravenously; intravenous access is per institutional standard of care for administration of PET tracer agents.

During the uptake period (15 minutes (± 10 minutes)), participants should be encouraged to hydrate and void frequently. Participants should be directed to void prior to being placed on the scanner.

Scanning will be initiated 15 minutes (± 10 minutes) post-injection. Scanner coverage should be set up to extend from vertex to mid-thighs. Low dose CT is to be used for anatomical correlation.

For Cohort 2, the same scanner must be used for the two scans unless there is a scanner failure or other technical issue.

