Primary Exclusion Criteria	
 1. Pregnant as determined by a pregnancy test as per institutional guidelines for individuals of child-bearing potential 2. Declining to use effective contraceptive methods during the study (for individuals of child-producing potential) 3. Need for emergent surgery that would be delayed by participation 4. Bacterial, viral, or fungal infections requiring systemic therapy, that are expected to impact FAP expression in the opinion of the sponsor or their designee 5. Serious co-morbidities and serious nonmalignant disease (e.g., hydronephrosis, kidney failure, liver failure, systemic or local inflammatory or autoimmune diseases or other conditions) that in the opinion of the investigator, physician of record and/or Sofie could compromise patient safety and/or protocol objectives. 6. Known diagnosis of an autoimmune disorder that is expected to impact FAP expression in the opinion of the sponsor or their designee 7. Patients receiving any other investigational agent within the past 28 days 8. Breastfeeding. Note: nursing parents are allowed if the potential participant commits to pumping breast milk and discarding it from injection to ≥ 24 hours from the time of the [⁶⁸Ga]FAPI-46 injection. 9. Known hypersensitivity to any excipients used in [⁶⁸Ga]FAPI-46: trace amounts of sodium acetate sodium ascorbate and/or hydrochloric acid
Test Article Administration and Imaging	Intravenous administration of radiolabeled [⁶⁸ Ga]FAPI-46 (5 mCi ± 2 mCi) as per institutional policies, administered 15minutes (±10minutes) prior to the initiation of the attenuation correction CT followed by the PET acquisition encompassing the participant's vertex through mid-thighs. Up to two [⁶⁸ Ga]FAPI-46 PET/CT scans may be performed per participant, depending on cohort.

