Data regarding the safety, dosimetry and efficacy of [⁶⁸Ga]FAPI-46 in humans have been extracted from published literature and has been received as personal communications from cited investigators and institutions. [⁶⁸Ga]FAPI-46 has been evaluated for biodistribution and dosimetry [Meyer et al, 2019]. [⁶⁸Ga]FAPI PET/CT imaging was shown to be safe for administration up to at least 200 MBq (5.4 mCi) [Meyer et al., 2019]. At 200 MBq (5.4 mCi), the whole-body effective dose including CT is 5.3 mSv, with CT contributing 3.7 mSv. Next, biodistribution was assessed for two of the six patients (one male and one female) [Meyer et al, 2019]. The highest average normal organ SUVmax at all time points was for the liver.

Tracer uptake in the tumor was rapid and had a greater retention time than normal organs; however, both mean SUVs decreased in all patients from the first to the last time points and tumor-to-background ratios increased over time. Therefore, in the totality of all the data, it was clearly determined that [⁶⁸Ga]FAPI-46 has a favorable dosimetry, avidity, and diagnostic isotope labeling profile with a biodistribution profile amenable for detection of FAP- expressing cells in patients with PDAC.

Lastly, but importantly, from preliminary diagnostic patient studies to date, there have been > 200 [⁶⁸Ga]FAPI-46 PET/CT scans with no reported adverse events [[name], Personal Communication. Essen University Hospital].

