6.2.3 Exploratory Efficacy Measures

The exploratory endpoints to be analyzed include:

- Number of lesions identified (0, 1, 2, 3 or more) through Standard of Care (anatomical (ie, CT, MR) and/or [¹⁸F]-FDG PET) and [⁶⁸Ga]FAPI-46 images
- Radiotracer accumulation observed in identified lesions SUV_{max}, SUV_{mean}, and tumor-to-background ratio (TBR) . If different background regions (such as muscle, blood, etc...) are used, TBR will be calculated and presented for all of them.
- Percentage change in [⁶⁸Ga]FAPI-46 PET SUV_{max} in the primary lesion between pre- and post-neoadjuvant therapy

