10.5 Study Drug [⁶⁸Ga]FAPI-46 Administration and PET Scan

The proportion and percentage of patients receiving each dose, along with descriptive statistics summarizing the dose amount and corresponding image quality of the PET scan, will be summarized by cohort for the SAS.

A listing displaying each dose (single dose in Cohort 1 and 2 doses in Cohort 2) of [⁶⁸Ga]FAPI-46, including the date and time of study drug administration, dose (mCi), date of image, imaging start time, and image quality will be provided using the SAS.

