10.6.5.1 PET Intensity

Descriptive analyses will be performed on PET intensity parameters and the following summaries will be produced:

- SUV_{max}, SUV_{mean}, and TBR in identified lesions using PET scan (EFFF1).
- SUV_{max}, SUV_{mean}, and TBR in identified lesions using PET scan and correlated with conventional [¹⁸F]-FDG PET scan for the same lesion if data is available. The correlation between [⁶⁸Ga]FAPI-46 PET and [¹⁸F]-FDG PET scan will be analyzed by Pearson's correlation test. The correlation coefficient and 95% CI will be provided (EFFF3).
- SUV_{max}, SUV_{mean}, and TBR differences between pre-NAT and post-NAT in the primary lesion for Cohort 2 using PET scan (EFFF4).

10.6.5.2 Tumor Lesions Detected by [⁶⁸Ga]FAPI-46 PET in Comparison with CT/MRI and/or [¹⁸F]-FDG PET

In addition to the primary lesion, a maximum of 3 LN was assessed by the reader. The number of identified LN detected by [⁶⁸Ga]FAPI-46 PET scan versus the standard of care assessments CT/MRI and/or [¹⁸F]-FDG PET, will be presented for the EFFF3 by cohort and visit, including pre-NAT and post-NAT differences for Cohort 2.

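### A Cohort 2 patient's two FAPI-46 scans can differ by up to 20 minutes in uptake time, and no planned SUV analysis takes uptake time into account

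*Protocol*

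**What the plan says.** Protocol 7.1.14 sets the timing: "Scanning will be initiated 15 minutes (± 10 minutes) post-injection". The Synopsis and Protocol 6.3.2 give the same window. The Synopsis anchors it to the CT, with the tracer given "prior to the initiation of the attenuation correction CT followed by the PET acquisition encompassing" the body, so the pancreas itself is imaged somewhat after the recorded start.

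For comparability of the two Cohort 2 scans, Protocol 7.1.14 has one rule: "For Cohort 2, the same scanner must be used for the two scans unless there is a scanner failure or other technical issue". Uptake time is not mentioned there. Protocol 7.1.12 refers to an imaging manual for technical detail; that manual is not among the documents.

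On the effect of time, Protocol 4.4 says of earlier human data that "both mean SUVs decreased in all patients from the first to the last time points and tumor-to-background ratios increased over time". It gives no time points and no rates.

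The SAP uses SUV in these places:
- 6.2.3: percentage change in SUVmax "in the primary lesion between pre- and post-neoadjuvant therapy".
- 10.6.5.1: SUVmax, SUVmean and TBR "differences between pre-NAT and post-NAT in the primary lesion for Cohort 2 using PET scan", in EFFS4. That set (7.1.2.4) requires interpretable scans of the same lesion before and after therapy and has no timing criterion.
- 10.6.3: Spearman correlation of SUVmax, and of SUVmean, with H-score.
- 10.6.5.1: Pearson correlation of FAPI-46 with FDG PET, where FDG data exist.

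None of these includes uptake time. The ingredients appear only in a patient listing in SAP 10.5, "including the date and time of study drug administration, dose (mCi), date of image, imaging start time, and image quality". The interval between the two times is not derived or summarised.

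**The concern.** The before/after comparison in Cohort 2 has no control group. Its purpose is to see whether neoadjuvant therapy perturbs FAPI-46 uptake. If SUV and TBR depend on time since injection, as the protocol's own summary says, then part of any observed change may come from the clock. The plan guards against a change of scanner but, in the protocol and SAP, not against a change of uptake time.

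Two consequences need to be kept apart. A mismatch that varies haphazardly from patient to patient makes each individual percentage change less trustworthy and widens the spread. A mismatch that runs in one direction, with Visit 3 scans tending to start later or earlier than Visit 1 scans, also shifts the group mean, and that shift would be read as a therapy effect.

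The secondary SUV versus H-score correlation uses one scan per patient, but patients may have been scanned at different uptake times. Variation unrelated to H-score tends to pull the correlation towards zero.

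**Working it through.** **The plan's own figure.** The only power statement is 92.7% for sensitivity (SAP 6.1.2: n = 60, performance goal 0.75, true value 0.90, one-sided 0.05). It reproduces. The z test first rejects at 51 of 60, where z = (51/60 − 0.75)/√(0.75 × 0.25/60) = 1.789, and the exact binomial power there is 0.9269. The calculation contains no SUV quantity, so this point leaves it alone.

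**Step 1: the permitted mismatch.** Earliest start 15 − 10 = 5 minutes; latest 15 + 10 = 25 minutes. The largest difference between two compliant scans is 25 − 5 = 20 minutes.

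**Step 2: spurious change in tumour SUV.** The documents give no drift rate, so k is an assumption, taken as a fall of 0.5% to 2% per minute. With no true therapy effect and a second scan Δ minutes later in uptake time, the apparent change is exp(−kΔ) − 1. For an earlier second scan it is exp(kΔ) − 1.

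| Mismatch Δ | Later second scan, k = 0.5% to 2% | Earlier second scan, k = 0.5% to 2% |
|---|---|---|
| 20 min (maximum) | 0.905 to 0.670: −10% to −33% | 1.105 to 1.492: +11% to +49% |
| 6.7 min | 0.967 to 0.875: −3% to −12% | 1.034 to 1.143: +3% to +14% |
| 5 min | 0.975 to 0.905: −2% to −10% | 1.025 to 1.105: +3% to +11% |

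The 6.7-minute row is the mean absolute difference, 20/3, if start times were spread evenly over the window and were independent between visits. That too is an assumption.

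A gentler set of assumed drifts, 2% to 10% per 10 minutes, gives −4.0% to −19.0% for a scan 20 minutes later and +4.1% to +23.5% for one 20 minutes earlier.

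**Step 3: TBR.** The ratio depends on two unknown rates. If background clears with half-time T, its factor over 20 minutes is 2^(−20/T), and the TBR ratio of a later to an earlier scan is exp(−20k) × 2^(20/T):
- T = 40 min: 0.905 × 1.41 = 1.28 down to 0.670 × 1.41 = 0.95
- T = 20 min: 0.905 × 2 = 1.81 down to 0.670 × 2 = 1.34
- T = 10 min: 0.905 × 4 = 3.62 down to 0.670 × 4 = 2.68

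Across these assumptions the ratio runs from about 0.95 to 3.6. No single fold-change can be defended.

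**Step 4: noise or bias.** If the uptake-time difference averages zero across patients, the group-level change is noisier but has no appreciable timing shift. If Visit 3 scans start, say, 5 minutes later on average, the group shift is about the 5-minute row above. The planned outputs contain no by-visit summary of uptake time from which to tell these cases apart.

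**The case against.** The strongest reply has four parts.

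First, the imaging manual may already require matched timing. That is possible, and the claim is limited to the protocol and SAP. A rule there would not fill the gap in the SAP, since no planned analysis would show whether it was followed.

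Second, the rates are invented. Protocol 4.4 gives neither slope nor time points. It also describes tumour uptake as rapid and retained longer than in normal organs, which argues against large drift in tumour SUV. This stands: neither the size nor the direction of drift between 5 and 25 minutes is documented, and the ranges above are illustrations.

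Third, the stakes are limited. The pre/post comparison is exploratory and descriptive, and 20 minutes is the extreme case. The primary endpoint uses the reader's positive or negative call. All of this stands.

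Fourth, both times are listed for each scan, so a reader could work out the mismatch by hand. That is true, but it leaves the interpretation to chance.

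Some stronger readings are tempting and are not supported:
- A reader might infer that the neoadjuvant result will be biased. That needs a systematic timing shift between visits, and nothing in the documents shows one.
- A reader might infer a 1.4- to 4-fold artefact in TBR. That comes from holding tumour SUV constant, whereas Protocol 4.4 says SUVs fell.
- A reader might treat SUVmax change as the sole measure of the therapy effect. SAP 10.6.5.1 also reports SUVmean and TBR, and 10.6.5.2 reports lymph-node counts.
- A reader might call the H-score correlation a key secondary endpoint. The SAP simply calls it secondary.

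**Conclusion.** The point holds as a worthwhile, inexpensive improvement to the SAP. It is not a threat to the trial's main conclusion. What rests on the text alone is that the window allows a 20-minute difference between a patient's two scans, that the protocol and SAP match those scans only on scanner, and that no SUV analysis uses uptake time although it can be derived from collected data.

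The size rests on assumption. At 0.5% to 2% per minute, the maximum mismatch alone gives −10% to −33% or +11% to +49% in SUV, and smaller mismatches give proportionately less. Individual pre/post changes and the H-score correlation are exposed to noise in any case; the group-level change is biased only under a systematic visit difference. The documents do not give the number of Cohort 2 patients, so the effect on the precision of the group mean cannot be worked out.

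**What to change.** Three changes to the SAP:

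1. **Section 10.5.** Derive uptake time (imaging start minus injection time) for every scan and summarise it by cohort and visit. State whether imaging start means the CT or the PET acquisition.
2. **Section 10.6.5.1.** Show each patient's difference in uptake time beside the pre/post changes in SUVmax, SUVmean and TBR. Repeat those summaries in pairs with similar uptake times. Fix the cut-off before the SUV data are analysed; 5 minutes is one example, and under the assumed rates it would limit the timing artefact in SUV to about 2% to 11% in either direction.
3. **Section 10.6.3.** Add, as a sensitivity analysis, the partial Spearman correlation of SUVmax and of SUVmean with H-score given uptake time.

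The cost is a little programming and fewer Cohort 2 pairs in the repeat. No new data are needed, and the sample size and primary analysis do not change.

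No change to Protocol 7.1.14 is proposed. SAP 6.1 describes the scans as already acquired, so a new matching rule would matter only if patients remain to be scanned.
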